2.2. Randomization

Participants will be stratified by site and randomly assigned 1:1 to the two intervention strategies within 24 hr of hospital admission. The Data Coordination Center (DCC) will provide a secure unpredictable allocation sequence (e.g. A B B A ...) which will be programmed into a secure electronic study tracking system for assignment of each accrued participant. The sequences will be generated using block size of two to four to maximize balance between arms throughout accrual while ensuring the sequences remain unpredictable. As patients consent to study participation, clinical-research staff will assign the next available study ID number in sequence, identify the allocated intervention arm, and inform participants and their families of the assignment. In turn, the clinical research staff will provide the linked study ID number and Medical Record Number to the DCC, which will store this Personal Health Information in a HIPAA-compliant manner along with the intervention assignment.

3. Study Procedures

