AIM 2: Safety of LCR vs. HCR during initial hospitalization. We hypothesize that LCR and HCR will *not* differ by *incidence of* 2A) hypophosphatemia (<3 mg/dL), 2B) hypomagnesaemia (≤ 1.7 mg/dL), and 2C) hypokalemia (<3.5 mEq/L).

AIM 3: Cost-effectiveness (CE) of LCR vs. HCR. We hypothesize that HCR will be more cost-effective than LCR, as determined by cost (including costs of initial and re-hospitalizations, 12 mo follow-up, other care, and safety/adverse events (AEs) and effectiveness per adolescent recovered (defined in AIM 1A and B).

2. Statistical Methods

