Aim 1B: Secondary (short-term) efficacy outcome: Time to restore and maintain medical stability in hospital is defined as days to reverse the medical instability indicators for hospitalization in adolescents with eating disorders. A six-point index will adjudicate daily medical stability: 1.) 24-hour heart rate (HR) ≥ 45 bpm, 2.) systolic blood pressure (SBP) ≥ 90 mmHg, 3.) temperature $\geq 35.6^\circ$ C, 4.) orthostatic increase in HR ≤ 35 bpm, 5.) orthostatic decrease in systolic BP ≤ 20 mmHg, and 6.) $\geq 75\%$ of mBMI. Each of the six criteria were scored as "1" if met, "0" if unmet and missing (not scored) if not measured. Medical stability was considered restored when all criteria were stable for 24 hours, allowing a maximum of two missing values (i.e. participants were considered stable if meeting 4 of 4, 5 of 5 or 6 of 6 measured criteria). All randomized participants who receive at least one day of treatment, including those who withdraw at any time during the refeeding intervention, will be included in the mITT analysis. Specifically, survival analysis with log rank test will compare time to achieve medical stability by arm while accounting for the correlation within sites; participants who do not meet stability criteria by hospital discharge will be right-censored. In case of any important unbalanced covariate at baseline, Cox proportional hazard ratio model will be used to control for the potential bias due to the confounder. Additionally efficacy outcomes will include the proportion achieving medical stability in each arm, change in %mBMI as compared to baseline, and time to restore HR.

Aim 2. Safety: Primary indicator of safety will be incidence of the following electrolyte abnormalities during hospitalization: 2A) hypophosphatemia (<3 mg/dL), 2B) hypomagnesaemia (≤ 1.7 mg/dL), 2C) hypokalemia (< 3.5 mEq/L). These AEs will be tracked, recorded, reported to the DSMB for monitoring, and to the IRB and NIH as needed, according to the attached DSMP. Incidence of the electrolyte abnormalities and proportion receiving supplementation to correct electrolyte abnormalities will be compared by arm during hospitalization using Fisher's exact test. Additional safety outcomes: the proportion receiving electrolyte supplementation during the hospitalization between groups will be compared with Fisher's exact test; time to electrolyte nadir will be compared with Wilcoxon rank sum test.

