2.3. Power and Sample-size Considerations

Aim 1. Based on studies of AN remission, **Table 2.A** shows that with $N=60$ per arm we have 80% power on 2-sided 0.05-level test to detect a 20% difference (8% vs. 28%) if data were cross-sectional ($\rho=1$). Our longitudinal data will allow detection of smaller effects, especially if the correlation among outcomes is low ($\rho < 0.8$). We anticipate 85% retention and non-differential dropout by arm. Since **time to medical stability** is also expected to differ by at least 12% (**Table 2.B.**), we will be adequately powered for Aim 1B.

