2.2 Outcomes	
Amendment 1: End-point for AIM 1B shortened to in hospital treatment period
 
Rationale: To match the timeframe for the safety outcome and to better capture the efficacy of this relatively short intervention (less than 2 weeks in hospital) within a long, open follow-up trial. Further, to allow timely dissemination of findings. [Citation: IOM guideline, Sharing Clinical Trial Data: Maximizing Benefits, Minimizing Risk, pg 118: Investigators “may publish the primary trial endpoints despite ongoing longer-term participant follow-up; in this case, the last participant’s last visit may not occur for some time, and hence the full analyzable data set may not be complete at the time of the original publication.”]
 
Timeframe for AIM 1B specified as 2 weeks and posted on clinicaltrials.gov
 
Project officer, [name] approved analysis of short-term (in-hospital) outcomes by arm (DSMB notified 7/03/19, randomization code was broken)
 
Short-term database locked
	06/30/2015 05/26/2019 07/31/2019
2.2 Outcomes	
Amendment 2: Analytic approach for AIM 1B changed from mixed effects regression modeling to survival analysis
 
Rationale: survival analysis chosen to examine time to restore medical stability in hospital (amended AIM 1B), rather than mixed effects regression modeling to examine medical stability over 12-month follow-up. This is a more appropriate approach to assess “time to” outcome, which accounts for the variable lengths of hospital stay and allows participants who were discharged before medical stability was restored to be right-censored.
 
Change in “time to” analysis documented in NIH Progress Report
 
Data Coordination Center documented decision to use survival analyses for AIM 1B
	05/05/2017 10/17/2017
2.2 Outcomes	
Amendment 3: Analytic approach for AIM 2 (safety) changed from Cox regression modeling to basic non-parametric testing
 
Rationale: Originally planned approach (Cox regression models) assumed high incidence electrolyte abnormalities based on prior studies reporting rates up to 48%. However, ongoing AE monitoring during the trial revealed very low incidence and therefore basic parametric methods were chosen to allow clinical interpretation of the results.
 
DSMB reports since 2017 (signed by DSMB members and sent to POs, [name] and [name])
	02/17/2017 02/20/2018 02/15/2019

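### Aim 2's Fisher exact test is valid but well below its nominal level when events are few; Boschloo's exact test with an interval would recover sensitivity to harm at little cost

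*Combined protocol and SAP*

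**What the plan says.** SAP section 1 frames Aim 2 as a hypothesis of no difference: "We hypothesize that LCR and HCR will *not* differ by *incidence of* 2A) hypophosphatemia", and likewise for hypomagnesaemia and hypokalemia. SAP section 2.2 makes these three abnormalities the primary indicator of safety and sets the test: "Incidence of the electrolyte abnormalities and proportion receiving supplementation to correct electrolyte abnormalities will be compared by arm during hospitalization using Fisher"'s exact test.

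Appendix Table 2, Amendment 3, explains why Cox regression was dropped. The earlier approach "assumed high incidence electrolyte abnormalities based on prior studies reporting rates up to 48"%, whereas "ongoing AE monitoring during the trial revealed very low incidence". No incidence figure is given.

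The SAP states no significance level, power, margin or confidence interval for the Aim 2 difference. The only stated level is in the Aim 1 paragraph of section 2.3, where with 60 "per arm we have 80% power on 2-sided 0.05-level test to detect a 20% difference (8% vs. 28"%). Allocation is 1:1, stratified by site (protocol section 2.2).

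**The concern.** Fisher's test conditions on the total number of events. When that total is small, only a few p-values are attainable, and the largest one at or below 0.05 is often much smaller than 0.05. The test then rejects a true null far less often than its label says, and it also rejects a false null less often than it could.

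In most comparisons such conservatism works against the investigators' hypothesis. In Aim 2 the hypothesis is that the arms do not differ, so a test that misses real differences works in its favour. What is at stake is the chance of detecting an excess of electrolyte abnormalities in one arm, in the comparison that carries the trial's main safety statement.

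**Working it through.** **Inputs.** From the documents: Fisher's exact test (SAP 2.2); 60 per arm and two-sided 0.05 (SAP 2.3, Aim 1); 1:1 allocation (protocol 2.2). Assumed: the same 0.05 level for Aim 2; incidence of 1–10%, with a wider range shown; about 60 per arm analysed, because Aim 2 is in-hospital and the 15% loss by 12 months does not apply. Unequal arms of 58 and 61 are a sensitivity check, not a documented count.

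**The plan's own figure (Aim 1).** With 8% vs 28% and 60 per arm, the mean rate is 0.18 and the pooled SE is √(2 × 0.18 × 0.82 / 60) = 0.0701. Then 0.20/0.0701 − 1.960 = 0.891, and Φ(0.891) = 81.4%, close to the stated 80%. By exact enumeration of the same case, Fisher has 77.1% power and Boschloo 81.0%.

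**Method for Aim 2.** For every pair of event counts (x₁, x₂), compute the two-sided Fisher p-value by summing the probabilities of tables no more likely than the one observed. The probability of rejection is Σ Bin(x₁; n₁, p₁) · Bin(x₂; n₂, p₂) over the tables with p ≤ 0.05. With p₁ = p₂ this is the true size; otherwise it is power. Boschloo uses the same ordering, but raises the cut-off on the Fisher p-value as far as possible while the maximum size over all common rates stays at or below 0.05. At 60 per arm the cut-off is 0.0665 and the maximum size is 4.9%.

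**True size, 60 per arm**

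| Common incidence | Fisher | Boschloo |
|---|---|---|
| 1% | <0.01% | 0.04% |
| 2% | 0.08% | 0.4% |
| 3% | 0.3% | 1.2% |
| 5% | 1.05% | 2.7% |
| 8% | 1.8% | 3.3% |
| 10% | 2.2% | 3.4% |
| 20% | 2.8% | 4.0% |
| 48% | 3.5% | 4.5% |

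Fisher's maximum over all rates is about 3.5%.

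**Power, 60 per arm**

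| Rates | Fisher | Boschloo | Gain (points) |
|---|---|---|---|
| 2% vs 10% | 27.7% | 39.5% | 11.8 |
| 2% vs 12% | 42.6% | 54.5% | 11.9 |
| 5% vs 15% | 32.6% | 39.2% | 6.6 |
| 5% vs 20% | 62.7% | 67.9% | 5.2 |
| 10% vs 25% | 49.4% | 54.8% | 5.4 |

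The gain is smaller in some other cases: 10% vs 20% goes from 24.7% to 29.0%, and 5% vs 25% from 84.5% to 87.4%.

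**In event counts.** For 5 vs 0, Fisher p = 2 × (60·59·58·57·56)/(120·119·118·117·116) = 0.057, not significant. For 6 vs 0, multiply by 55/115: p = 0.027. Fisher therefore first rejects at 6 vs 0, 8 vs 1 and 10 vs 2; Boschloo at 5 vs 0, 7 vs 1 and 9 vs 2. The difference is one event.

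**Sensitivity to arm size.** With 55 per arm Fisher's size at 5–10% incidence is 0.9–2.0%, and power at 5% vs 15% rises from 28.5% to 38.5% with Boschloo. With 58 and 61, Fisher's size is 1.9–3.4% at 5–10% incidence (maximum 4.3%). If the higher rate is in the larger arm, the gain is about 4–7 points (5% vs 15%: 35.5% to 40.5%). If it is in the smaller arm, the gain over the five tabulated pairs of rates runs from about 3 points (5% vs 20%: 69.7% to 72.4%) to about 10 (2% vs 10%: 39.0% to 49.3%).

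**Three electrolytes.** Taking three independent unadjusted tests, the chance of at least one false positive is 1 − (1 − size)³. At 5% incidence it is 3.1% with Fisher and 7.8% with Boschloo; at 10% it is 6.4% and 9.8%.

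**The case against.** Fisher's test is standard for sparse 2×2 tables and never exceeds its level. There is also a randomisation argument for it: under the sharp null each participant's outcome is the same in either arm, so conditioning on the event total is natural. Both points stand. A reader might infer that the plan uses a wrong test; it does not. The matter is efficiency.

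A reader might also take 1–2% as the trial's actual error rate. That range needs incidence of roughly 5–10%, equal arms of 60 and an assumed 0.05 level, and the documents fix none of these for Aim 2.

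Nor do the documents show that Fisher was chosen to favour a null result. Amendment 3 does not name the test, and its stated reason is clinical interpretability at low incidence.

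Boschloo is itself well below 5% when events are rare, gains about one event, and still misses 5% vs 15% about 61% of the time (100 − 39.2). This stands, and it limits the benefit. The calculation also pools sites despite stratified allocation, but so does the Fisher comparison as written.

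The overall false-positive chance across the three electrolytes does rise, as shown above. Per-test control at 5% is kept, and the SAP states no multiplicity adjustment for Aim 2 with either test.

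Finally, Appendix Table 2 records that the randomisation code was broken (DSMB notified in July 2019) and that the short-term database was locked on 31 July 2019. Moving to a less strict rejection rule after that is more than a wording change. This governs how the result should be labelled, not whether it is worth reporting.

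**Conclusion.** The point holds as an optional, nearly free improvement. At 60 per arm and an assumed two-sided 0.05 level, Fisher's true size is about 0.1–0.3% at 2–3% incidence, 1–2% at 5–10%, and no more than about 3.5% anywhere. Boschloo rejects every table that Fisher rejects and some more, keeps each test at or below 5%, and adds about 5–12 power points in the five tabulated scenarios. With slightly unequal arms the conservatism is smaller, and the gain is typically about 4–7 points, depending on which arm has the higher rate. Because Aim 2 hypothesises no difference, the sensitivity lost with Fisher favours the hoped-for result.

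It would go too far to say that changing the test lets a non-significant result support the Aim 2 hypothesis. Power stays modest with either test and the SAP gives no margin. Only a confidence interval shows which differences the data exclude.

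**What to change.** In SAP section 2.2, Aim 2, name Boschloo's unconditional exact test for the three electrolyte incidence comparisons and the supplementation comparison. State the two-sided 0.05 level, and define the two-sided version (ordering by the two-sided Fisher p-value) so that software defaults do not decide it. For each comparison report the risk difference with an unconditional exact 95% confidence interval, and base statements about similarity on that interval rather than on the p-value. Say whether the three tests are adjusted for multiplicity.

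If outcomes by arm have already been seen, keep Fisher as the planned test and report Boschloo beside it as a labelled sensitivity analysis, with the intervals.

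The cost is a few lines of SAP text and minimal programming, with no extra participants or data. The downside is a somewhat higher chance of at least one false positive across the three unadjusted tests.

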A high energy liquid supplement ("formula") providing 1.5 kcal per mL (360 kcal per 240 mL can) will be used orally as needed to replace kcal refused in meals or snacks per a standard calorie replacement protocol. We previously reported a greater than 98% concordance between kcal prescribed and actual kcal ingested using this method, as well as an equal proportion of kcal intake from formula in LCR and HCR groups. This finding supports our clinical observation that HCR meals can be completed without additional reliance on drinking formula. However, most AN patients do experience discomfort during refeeding and therefore all participants will receive SOC meal support including emotional support and techniques such as distraction. All beverages will be weighed and measured before placement on the tray, with a 1.5 L per day free water restriction. Room sitters will observe intake of all meals/snacks and remain in the room for 45 min afterwards.

c. Monitoring of electrolytes: Blood for electrolytes will be obtained between 5 and 7 am every 24hr for the first 7 days and more frequently if needed. Since the risk of refeeding decreases after the first week, electrolytes will be monitored every other day starting on day 8 unless there is continued evidence of abnormalities.

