e. Study time points: Participants will be followed prospectively in hospital with daily measures of calorie and supplement intake and weight from admission through discharge. Patients will be discharged when medically stable, with the primary criterion of heart rate ≥ 45 bpm for least 24 hr. Full medical stability defined as HR ≥ 45 bpm for 24 hrs, temperature ≥ 35.6°C for 24 hrs, ≥ 75% of mBMI, BP ≥ 90/45 mmHg for 24 hrs or if systolic BP < 90 then asymptomatic and all else stable, orthostatic change in HR ≤ 35 bpm or if > 35 then asymptomatic and all else stable; and orthostatic change in SBP ≤ 20 mmHg or if > 20 then asymptomatic and all else stable.

Timing of Procedures: Table 1

	INPATIENT			OUTPATIENT FOLLOW---UP				
	Admit	Daily	DC*	10 dy	1 Mo	3 Mo	6 Mo	12 Mo
MEDICINE/NURSING PROCEDURES								
Weight	SOC	SOC	SOC	X	X	X	X	X
Height	SOC			X	X	X	X	X
Vital Signs	SOC	SOC	SOC	X	X	X	X	X
Electrolyte monitoring ¥	SOC	X	SOC					
NUTRITION PROCEDURES								
24---hr food recall	X			X	X	X	X	X
QUESTIONNAIRE ADMINISTRATION								
EDE-Q	X		X		X	X	X	X
HCUMS survey				X	X	X	X	X
Demogr & Eating Disorder	X							

Follow-up form				X	X	X	X	X
----------------	--	--	--	---	---	---	---	---

* DC = discharge; SOC = Standard Of Care; Rnd = Randomization; ¥ SOC is every other day; we will monitor daily as part of Aim 2.

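### Time to electrolyte nadir has no common observation window, so a difference in length of stay can register as an electrolyte effect; the depth of the nadir is not compared

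*Combined protocol and SAP*

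**What the plan says.** SAP section 2.2, Aim 2, names the main safety measure: "Primary indicator of safety will be incidence of the following electrolyte abnormalities during hospitalization". The three abnormalities are yes/no thresholds for phosphorus, magnesium and potassium, compared by Fisher's exact test. Among the additional safety outcomes are the proportion receiving supplementation (Fisher) and the nadir: "time to electrolyte nadir will be compared with Wilcoxon rank sum test". Nothing states the days over which the nadir is sought, how tied lowest values are dated, or what is done with patients whose stays differ.

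Protocol section 3.1.c sets the draws: "Blood for electrolytes will be obtained between 5 and 7 am every 24hr for the first 7 days and more frequently if needed". After that, "electrolytes will be monitored every other day starting on day 8 unless there is continued evidence of abnormalities". The footnote to Table 1 reads differently: "SOC is every other day; we will monitor daily as part of Aim 2". Table 1 schedules electrolytes in the inpatient columns only.

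On the end of stay, protocol section 3.1.e says "Patients will be discharged when medically stable", with heart rate as the leading criterion. SAP section 2.3 expects medical stability to differ by at least 12 percentage points, and every row of Table 2.B has HCR higher. For Aim 1B, Appendix Table 2 (Amendment 2) justifies survival analysis partly because it "accounts for the variable lengths of hospital stay". Time to nadir gets no such treatment.

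**The concern.** The day of the lowest value can only be as late as the last draw, and the last draw is fixed by discharge. Where a patient's values show no strong trend, the minimum can fall on any draw day, so a longer stay pushes the nadir later by chance alone. If one arm goes home sooner, its nadir will tend to come earlier even when electrolytes behave identically in both arms. The Wilcoxon test treats that day as fully observed and so partly tests length of stay.

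An earlier nadir under HCR would be easy to misread as a refeeding effect. Meanwhile, how far values fell, which the same samples contain, enters only through the thresholds and receipt of supplementation.

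**Working it through.** The plan gives no error rate or power for this outcome, so there is no figure to reproduce.

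**Inputs from the documents.** 60 per arm and a two-sided 0.05 test (SAP 2.3); 1:1 allocation (protocol section 2); daily draws to day 7 then alternate days (protocol 3.1.c), or daily throughout (Table 1 footnote); stays under two weeks (Appendix Table 2, Amendment 1).

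**Assumed, because the documents do not give them.** Stay by arm, its SD, the shape of the electrolyte course, and lag-1 correlation 0.5 between days.

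**Step 1, arithmetic for flat values.** If values are exchangeable over days, each draw is equally likely to be the lowest, so expected nadir day = mean of the draw days.
- Daily draws, stay L: (L + 1)/2. For 12 days, 13/2 = 6.5; for 9 days, 10/2 = 5.0. Gap 1.5 days.
- Alternate days from day 8: for 12 days, (1+2+...+7+8+10+12)/10 = 58/10 = 5.8; for 9 days, (1+2+...+8)/8 = 36/8 = 4.5. Gap 1.3 days.

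The gap arises with no electrolyte effect.

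**Step 2, false rejection by simulation.** Identical electrolyte process in both arms, 60 per arm, stay SD 2 days. The dip is centred on day 3, equal in both arms, and measured in within-patient SDs.

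| Mean stay | Course | Daily draws | Alternate days from day 8 |
|---|---|---|---|
| 12 vs 9 | flat | about 57% | 29% to 40% |
| 12 vs 9 | dip of 1 SD | 21% to 23% | 14% to 18% |
| 12 vs 9 | dip of 2 SD | 7% | 5% to 6% |
| 12 vs 11 | flat | 9% to 10% | 7% |
| equal | flat | about 5% | about 5% |

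Ranges are over repeated simulations. The alternate-day range may partly reflect which alternate days are drawn. The dip rows also depend on the assumed width of the dip.

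**Step 3, a second set of assumptions.** Stay SD 3 days; phosphorus mean 4.0 mg/dL, within-patient SD 0.25. Mean stays HCR/LCR of 10/10, 9/11, 8/11 and 8/12 with flat values give 5%, 19%, 36% and 52% on the section 3.1.c schedule, and 4%, 23%, 47% and 70% with daily draws. Across the three unequal-stay settings:
- dip of 0.2 mg/dL: 11% to 27% (daily 12% to 42%);
- dip of 0.4 mg/dL: 6% to 12% (daily 10% to 17%);
- steady rise: 7% to 14% (daily 7% to 18%).

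**Step 4, does a common window repair it?** With flat values:
- Days 1-7: 4% to 6% at 12 vs 9 days (SD 2), but about 10% at 8/11 and 8/12 (SD 3), 11% at 11 vs 8 (SD 3), and 13% to 16% at 10 vs 7 (SD 2), because patients leave before day 7.
- Days 1-5: 4% to 6% across the settings examined. The level depends on nearly everyone still being in hospital.

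**Step 5, depth.** The lowest value over the whole stay is mildly affected too: a comparison of it rejects in 5% to 13% with flat values and unequal stays, against 4% to 6% inside a 5- or 7-day window. Any comparison of depth should therefore use the same window.

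**The case against.** The strongest reply is that the large rates need flat values and a stay gap of several days, and the documents establish neither. That stands. A reader might infer flat series from Amendment 3, which reports very low incidence of abnormalities. But incidence counts crossings of a cut-off. A patient can fall clearly and stay above it, and protocol section 3.1.d foresees declines within the normal range. Section 3.1.c also places the refeeding risk in the first week, which fits an early dip, and an early dip shrinks the artefact.

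A reader might also infer a 3-day stay gap from the expected difference in stability. SAP 2.3 gives percentage points, not days. Discharge turns mainly on heart rate rather than the six-point index, and Amendment 2 provides for patients discharged before stability. The link is real but loose.

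That the nadir is taken over each patient's own stay is itself inferred from inpatient-only draws. The SAP simply leaves the window undefined.

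On depth, thresholds plus supplementation are a legitimate safety set. A reader might infer a large loss of power: at 5% vs 15% crossing a cut-off, Fisher has about 33% power and a comparison of means about 91%. That contrast assumes a pure normal shift with equal SD and ignores treatment of low values. Its 15% also sits awkwardly with very low incidence. It does not support a claim about how much is lost in this trial.

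What survives is that the window is undefined, the test is exposed to stay differences, and no lowest value is compared.

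**Conclusion.** The point holds conditionally. As written, the Wilcoxon comparison of time to nadir can reject because stays differ, with no electrolyte effect. With assumed stays of 12 vs 9 days (SD 2) and 60 per arm, false rejection runs from about 57% (flat values, daily draws) through about 20% (modest equal dip) to 5% to 7% (clear equal dip). At a 1-day gap it is 7% to 10% even with flat values, and with equal stays there is no inflation. The documents do not say which case applies.

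The omission of nadir depth is a gap in the additional safety comparisons and does not undermine the primary one. Threshold incidence was barely distorted in the same simulations (3.5% vs 4.6% below 3 mg/dL, flat values, stays 8 vs 12 days). The plan rests no sample size or stated decision on nadir timing. The change is worth making, but the main safety conclusion does not depend on it.

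**What to change.** In SAP section 2.2, Aim 2:

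1. Derive the nadir for each electrolyte from the scheduled morning draws in an early window that nearly all patients in both arms complete. Days 1-5 is one choice. Days 1-7 is another, but only with a stated rule for patients discharged earlier. Choose the window from the pooled distribution of stay, without looking at results by arm.
2. State how tied lowest values are dated (for example, the first occurrence).
3. Add, as an additional safety comparison, the arm difference with 95% CI in the lowest value in that window, adjusted for the admission value. Note beside it that correction of low values can limit later falls.
4. Keep whole-stay time to nadir as description only, shown alongside length of stay by arm.
5. Reconcile protocol section 3.1.c with the Table 1 footnote on draws after day 7, since the schedule affects any whole-stay summary.

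The cost is some SAP wording and one extra model per electrolyte, on data already collected. The downside is that nadirs after the window are described and not tested. Appendix Table 2 records a lock of the short-term database, so if these analyses are added after that point they should be labelled post hoc.

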2.2. Outcomes

The primary analysis of the study adopts a modified intent-to-treat (mITT) approach to compare outcomes between randomized HCR and LCR participants who received treatment for at least one day. Patients who are ineligible post randomization, provide no assent after parent's consent, or withdraw before receiving any treatment, will not be included in the mITT analysis for reasons of data unavailability, ethics and clinical relevance. Sensitivity analyses will be conducted to check that 1) withdrawal patients are not different from patients in both groups included in mITT in baseline covariates; and 2) including withdrawal patients in the analyses will not change results and conclusion of mITT analyses. The sensitivity analyses will provide us

reassurance of mITT results.

Aim 1A: Primary (long-term) efficacy outcome. A (generalized) linear mixed-effects regression model (GLMM) will compare study arms with respect to achievement and maintenance of clinical remission. Clinical remission is defined as the combination of mBMI and EDE-Q score at mo 1,3,6,12 (separate analyses below) and measured at 1, 3, 6, and 12 months as 1) clinically remitted (yes or no) and 2) weight recovered (percent of mBMI). The models will include time, treatment group, time*treatment group interaction, and unbalanced baseline covariates if any as fixed effects, while sites and patients will be included as random effects to account for the correlation due to clustering. The time*treatment group interaction provides mITT effect of HCR compared to LCR on clinical remission over time. The average remission rates and scores and their 95% confidence intervals (CIs) will be estimated from the model. GLMM accounts for the fluctuating nature of mBMI and EDE-Q in AN and uses all available data with missing at random assumption, instead of a stronger assumption of missing completely at random required in other models. Aim 1 models will be supplemented with secondary analyses: (i) potential moderators at baseline (included in regression models as main effects and interactions with period and time), may include DSM-5 criteria and EDE-Q thresholds of risk and (ii) potential mediators at follow-up (included as time-dependent covariates), may include food recall (DDS and DVS), healthcare utilization, or incidence of AEs. In addition, separate mixed-effects models will analyze continuous versions of mBMI and EDE-Q to describe longitudinal trajectories.

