Aim 3. Cost Effectiveness (CE): A decision tree of treatment costs, AEs, health care utilized (including rehospitalizations), and remission will compare the CE between the two study arms. The main CE outcome is incremental cost per additional adolescent remitted. Health care utilization will be costed using national data sources such as acquisition costs for medications, Kids-HCUP for hospitalizations, CPT codes for physician visits and mental health visits, and internet-based costs for lab tests. We will use 2014 US costs and not charges. Indirect costs including missed school and workdays will be assessed and costed using national estimates of wages and salaries of this age group from the Bureau of Labor Statistics, in order to estimate loss of leisure time (school) or salary

time (work).

We will determine the incremental CE ratio (ICER) as:

$$\text{ICER} = \text{CostLCR-CostHCR}/\text{Number RecoveredLCR-Number RecoveredHCR}.$$

Effectiveness will also be indicated by cost of rehospitalizations avoided (ie, rehospitalizations in LCR-HCR). We will determine the net monetary benefit (NB) of each treatment option as: $\text{NB} = \text{Effectiveness} \times \text{Willingness To Pay (WTP)} - \text{Cost}$. A positive difference in NB between treatments indicates CE. We will also calculate an acceptability curve to demonstrate how parameter uncertainty affects the likelihood of selecting the optimal treatment at a given WTP threshold. Cost of treatment will be determined by initial hospitalization and 12 mo follow-up costs (not charges) including AEs and rehospitalizations. The HCUMS follow-up survey will assess indirect costs such as lost school and/or work (wages) using national data sources (see **C.2.c.(2)**).

Effectiveness will be determined per aim 1A; ICER will also use time (incremental cost per additional day of recovery time over 12 mo). Cost efficacy will be assessed with short-term outcomes at end of hospitalization. Per Aim 1B, cost-efficacy will be assessed with other short-term outcomes at the end of treatment (hospitalization period). Cost-efficacy will be defined as hospital cost or charges associated with length of stay; group differences will be compared with Wilcoxon rank sum test.

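### The Aim 3 ICER is written with numbers recovered and an unspecified cost, so it depends on arm size unless costs are arm totals and the analysed arms are equal

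*Combined protocol and SAP*

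**What the plan says.** In SAP section 2.2, Aim 3, a decision tree is planned and the target is stated: "The main CE outcome is incremental cost per additional adolescent remitted". The definition follows, introduced by "We will determine the incremental CE ratio (ICER) as". Its numerator is "CostLCR-CostHCR" and its denominator "Number RecoveredLCR-Number RecoveredHCR". No divisor for arm size appears, and cost is not described as a total or a mean.

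The same section later says "Effectiveness will be determined per aim 1A; ICER will also use time". Under Aim 1A the effectiveness quantity comes from a mixed model: "The average remission rates and scores and their 95% confidence intervals (CIs) will be estimated from the model".

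On rehospitalization, Aim 3 adds "Effectiveness will also be indicated by cost of rehospitalizations avoided", with a parenthesis that refers to rehospitalizations in LCR minus HCR. It also includes rehospitalizations in the cost of treatment. Net benefit is effectiveness times willingness to pay, minus cost; the effectiveness measure that enters it is not named.

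The analysis set is mITT. Participants found ineligible after randomization, those without assent, and those who "withdraw before receiving any treatment, will not be included in the mITT analysis" are left out. The table of SAP amendments lists no change to Aim 3, so this is current text.

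**The concern.** A number recovered is arm size multiplied by remission proportion. A difference between two such numbers therefore mixes a treatment effect with a difference in arm size, and it is zero under equal remission only when the arms are equal. A total cost has the same property. An analyst who follows the formula literally could report a cost per additional remission of the wrong size or sign, and could carry the same quantities into the net benefit and the acceptability curve.

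The main Aim 3 result is at stake. The Aim 1A remission analysis and the Aim 2 safety comparison are not affected. Brackets missing from the printed formula are not part of this point, since they may have been lost in typesetting.

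**Working it through.** The plan gives no ICER, cost or willingness-to-pay figure, so there is none to reproduce. The check evaluates the printed formula.

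**Inputs from the documents**
- 60 per arm; 8% (LCR) vs 28% (HCR): SAP section 2.3 and Table 2.A.
- 1:1 allocation stratified by site, blocks of two to four: Protocol section 2.2. An incomplete block of four can leave an imbalance of 2 at a site, so 4 over two sites: 62 vs 58.
- 85% retention, dropout taken as non-differential: SAP section 2.3.

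**Assumptions, not in the documents**
- Mean cost 20,000 (LCR) and 21,000 (HCR).
- Analysed splits of 54/60 and 51/60 (LCR/HCR).

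**Step 1. Denominator under equal remission.** Count difference = n_L × p − n_H × p, with p = 0.28:
- 60/60: 16.80 − 16.80 = 0
- 62/58: 17.36 − 16.24 = 1.12
- 54/60: 15.12 − 16.80 = −1.68

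The difference in proportions is 0 in every row.

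**Step 2. Denominator at the planned effect.** HCR minus LCR count, against 16.80 − 4.80 = 12.00 at 60/60:
- 62/58: 16.24 − 4.96 = 11.28 (−6%)
- 54/60: 16.80 − 4.32 = 12.48 (+4%)
- 51/60: 16.80 − 4.08 = 12.72 (+6%)

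The difference in proportions stays at 0.20. The relative shift is larger when the effect is smaller: in the last row of Table 2.A (22% vs 34%) the count difference is 20.40 − 13.20 = 7.20 at 60/60 and 19.72 − 13.64 = 6.08 at 62/58 (−16%).

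**Step 3. Arm totals over counts.** ICER = (n_L c_L − n_H c_H) / (n_L p_L − n_H p_H):
- 60/60: (1,200,000 − 1,260,000) / (4.80 − 16.80) = −60,000 / −12.00 = 5,000
- 62/58: (1,240,000 − 1,218,000) / (4.96 − 16.24) = 22,000 / −11.28 = −1,950
- 58/62: (1,160,000 − 1,302,000) / (4.64 − 17.36) = −142,000 / −12.72 = 11,164

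The per-participant ratio is (20,000 − 21,000) / (0.08 − 0.28) = 5,000 at any split. The numerator moves so much because, with arms of 60 + k and 60 − k, it equals 60(c_L − c_H) + k(c_L + c_H). At k = 2 that is −60,000 + 82,000 = 22,000: the full cost of a few extra participants outweighs the between-arm difference in mean cost.

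**Step 4. Mean cost over counts.** At 60/60: −1,000 / −12.00 = 83.3, against 5,000. The ratio is too small by a factor of 60, the arm size.

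**Step 5. Match with Aim 1A.** The effectiveness source is a model-estimated rate that uses all available data under missing at random. A number recovered is a different quantity, and the formula names none of the 1, 3, 6 and 12 month visits.

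**Step 6. Rehospitalization.** Suppose a saving d lowers cost and is also entered as effectiveness valued at 1 per unit of money. The net-benefit difference then gains d + d = 2d instead of d. This happens only if the two are combined.

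**The case against.** The best defence is that the formula is schematic. A decision tree normally evaluates both options for a common cohort, in which case numbers recovered would refer to the same cohort size and arm size would cancel. The reference to Aim 1A, whose output is a rate, points the same way. This is a fair guess at intent and it stands as such, but the SAP does not state a cohort size, and nothing else in it corrects the formula.

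The formula is also exact when costs are totals and the analysed arms are equal, which stands too.

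Three stronger readings are tempting and are not supported:
- A reader might infer that the 15% loss must unbalance the arms. SAP section 2.3 expects non-differential dropout, which gives about 51 vs 51 (60 × 0.85). No numbers are given for mITT exclusions. Imbalance beyond 62/58 is possible, not implied.
- A reader might infer that the ratio will be about 60 times too small. That requires mean costs over raw counts, a combination the SAP permits by silence but does not prescribe.
- A reader might infer that rehospitalization is counted twice. It is an additional indicator, the parenthesis may mean a count, and nothing says it enters the net benefit or is set against a total cost that contains it. The main remission-based ICER does not double count.

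**Conclusion.** The point holds as a defect of definition. No stated figure is miscalculated. As printed, the formula gives the intended ratio only with total costs and equal analysed arms, and neither condition is specified.

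The distortion of the denominator alone is modest at the planned effect: about 4% to 6% at 62/58 and at the assumed splits of 54/60 and 51/60. Under equal remission of 28% it is a spurious 1.1 remissions at 62/58, or 1.7 at 54/60. The larger risk is the numerator. If totals are used, an imbalance that the randomization itself allows can change the ICER greatly or reverse its sign, from 5,000 to −1,950 in the example. That size depends on the assumed costs of 20,000 and 21,000; the dependence on arm size does not.

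The rehospitalization issue is secondary and conditional. The plan should be changed, because the main Aim 3 result rests on this line, but the consequence is confined to Aim 3.

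**What to change.** In SAP section 2.2, Aim 3, replace the formula with:

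ICER = (mean cost per participant in HCR − mean cost per participant in LCR) / (proportion remitted in HCR − proportion remitted in LCR)

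State that both differences come from the same analysis set, that the proportions are the Aim 1A remission rates, and at which time point. State that net benefit and the acceptability curve use the same per-participant cost and effect.

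Define the rehospitalization effect as the number avoided per participant, say how rehospitalization cost is handled when that effect is used, and do not enter a cost as effectiveness in the net-benefit formula.

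The cost is a few lines of SAP text. No new data are needed.
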